## **4.3 STUDY TREATMENT AND OTHER TREATMENTS RELEVANT TO THE STUDY DESIGN**

The investigational medicinal products (IMPs) for this study are balovaptan and itraconazole.

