**Table 3 Causal Attribution Guidance**

Is the AE suspected to be caused by the study drug on the basis of facts, evidence, science-based rationales, and clinical judgment?	
YES (RELATED)	There is a plausible temporal relationship between the onset of the AE and administration of the study drug, and the AE cannot be readily explained by the subject's clinical state, intercurrent illness, or concomitant therapies; and/or the AE follows a known pattern of response to the study drug; and/or the AE abates or resolves upon discontinuation of the study drug or dose reduction and, if applicable, reappears upon re-challenge.
NO (NOT RELATED)	An AE will be considered related, unless it fulfills the criteria specified below. Evidence exists that the AE has an etiology other than the study drug (eg, pre-existing medical condition, underlying disease, intercurrent illness, or concomitant medication); and/or the AE has no plausible temporal relationship to administration of the study drug (eg, cancer diagnosed 2 days after first dose of study drug).

For subjects receiving combination therapy, causality will be assessed individually for each protocol-mandated therapy.

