6.0 Study Design

This study will be non-randomized, open-label, one-sequence, two-period within-subject study to investigate the effect of CYP3A inhibition on the PK of balovaptan in healthy male and female volunteers using itraconazole as a CYP3A inhibitor. The study will be conducted at 1 site in the Netherlands.

Subjects will be screened for eligibility for the study for up to 28 days before the first dose of study drug. In Period 1, eligible subjects will be admitted to the clinical research unit (CRU) in the afternoon of Day -1 and remain in the CRU until discharge in the morning of Day 11. There will be at least a 7-day washout between the last dose in Period 1 and the first dose in Period 2. After this washout period, subjects will return to the CRU on Day -1 of Period 2 and remain in the CRU until discharge on Day 21 of Period 2. For each study period, dosing will begin on Day 1. Subjects will receive the following study drugs in 2 periods over a total of 37 days:

[figure not shown]
Period 1:

- Days 1 to 10: oral balovaptan once daily (qd)
- Days 11 to 17: no study drug

Period 2:

- Days 1 to 5: 200 mg itraconazole twice daily, approximately 12 hours apart (on Day 5, only the AM dose of itraconazole will be administered)
- Days 6 to 20: balovaptan qd + 200 mg itraconazole qd

Figure 1 presents an overview of the study design. A schedule of activities is provided in [Appendix 2](#).

Figure 1 Study Schema

Abbreviations: bid = twice daily; PK = pharmacokinetics; qd = once daily

On Period 1 Day 10 and Period 2 Day 20, balovaptan will be dosed at the same time of day. On Period 2 Days 5 and 20 itraconazole will be dosed at the same time of day. On Period 2 Days 6 to 20, itraconazole will be administered in combination with balovaptan.

Subjects will undergo study assessments and procedures, including assessments of AEs and concomitant medications, vital signs, 12-lead ECGs, clinical laboratory evaluations and blood sampling for PK assessments and genotyping as per the schedule of assessments in [Appendix 3](#).

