7.0 Overview of Planned Analysis

7.1 Changes from Protocol

There are no changes from the protocol.

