17.1.1 Adverse Events

All AEs will be coded to the current version of Medical Dictionary for Regulatory Activities (MedDRA, the latest version) by F. Hoffmann-La Roche, Ltd.

All AE summaries will include only treatment emergent adverse events (TEAEs). Treatment-emergent adverse events are those which occur after the first dose of study drug. AEs starting prior to medication dosing in the first period will be regarded as pre-dose AEs (i.e. non-TEAEs).

TEAEs occurring following dosing in a specific analysis period but before dosing in the next analysis period will be attributed to that specific analysis period, thus to the last treatment received. If the time is missing for an AE on a dosing day then the AE will be attributed to the treatment given on that day.

All adverse events (including non-TEAEs) recorded on the eCRF will be listed. Pre-dose AEs will be presented in a separate listing. In addition, a separate listing of AEs leading to withdrawal from study will be provided.

TEAEs will be tabulated by system organ class and preferred term: one table with all TEAEs (number and percentage of subjects) overall and by treatment; one table with related TEAEs (number and percentage of subjects) by treatment; one table with all TEAEs (number and percentage of subjects) by treatment and relationship to study drug; one table with TEAEs (number and percentage of subjects) by treatment and severity.

Subjects are counted once, per preferred term per treatment, for the most severe of multiple occurrences (in case of severity) or most drug-related event (in case of relationship) of a specific MedDRA term. AEs whose causal relationship was characterized as 'Yes'/'No' will be regarded as being related/not related to the study medication.

The following missing data will be imputed as defined (for calculations only / will not be presented):

- Missing AE start and / or end times for the calculation of onset and duration will be assumed to be at 00:01 for a start time and 23:59 for end times
- Missing AE severity or relationship will be assumed to be severe or related, respectively
- Missing AE start times for the determination of treatment emergence will be assumed to occur after treatment unless partial date documents the AE as happening prior to treatment
- Missing AE start times for the determination of treatment assignment will be assumed to occur after treatment on the recorded date one minute after dosing

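### During coadministration causality is collected for each drug, but the SAP tabulates one relationship to study drug and gives no rule when the two answers differ

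*SAP*

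**What the plan says.** Protocol 4.3 names two investigational products: "The investigational medicinal products (IMPs) for this study are balovaptan and itraconazole". Under Protocol 5.3.4 the investigator answers yes or no on relationship to study drug, and a note to Table 3 adds: "For subjects receiving combination therapy, causality will be assessed individually for each protocol-mandated therapy".

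SAP 6.0 uses study drugs for both agents. Its regimen list opens with "Subjects will receive the following study drugs in 2 periods over a total of 37 days" and includes the itraconazole run-in as well as the combination. SAP 9.2.2 makes itraconazole alone a treatment in its own right (Treatment 2).

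For relationship, SAP 17.1.1 plans two tables: "one table with related TEAEs (number and percentage of subjects) by treatment", and "one table with all TEAEs (number and percentage of subjects) by treatment and relationship to study drug". Yes and No answers "will be regarded as being related/not related to the study medication". A missing relationship is set to related, with no drug named. SAP Appendix 4 lists the two outputs as Tables 14.3.1.2 and 14.3.1.3 and has no per-drug version. SAP 9.5 says that no table shells will be supplied.

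**The concern.** From Study Day 6 of Period 2 an adverse event carries two causality answers by design, and the planned tables have room for one. No section of the SAP says which answer feeds the table, or how a No for one drug and a Yes for the other are combined.

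The secondary objective (SAP 5.2) is the tolerability of balovaptan given alone and given with itraconazole. In the balovaptan-alone column, related can refer only to balovaptan. If it refers to either drug in the combination column, the columns use different definitions, and a higher count in the second could come from the inhibitor's own side effects. The overlap is real: Protocol 1.3 reports headache as the most frequent adverse event with balovaptan and also lists headache among the effects of itraconazole. The per-drug answers are collected so that such cases can be told apart, and the planned display does not use them.

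**Working it through.** The plan states no figure on this point, so the main check is a comparison of texts.

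**Step 1: which events are affected.** The note to Table 3 applies to subjects on combination therapy, which is Study Period 2, Days 6 to 20. Days 1 to 5 are itraconazole alone, and Period 1 is balovaptan alone.

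**Step 2: the possible answers for one event, under the two readings of study drug.**

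| Balovaptan | Itraconazole | Counted if study drug is either agent | Counted if study drug is balovaptan only |
|---|---|---|---|
| No | No | not related | not related |
| Yes | No | related | related |
| Yes | Yes | related | related |
| No | Yes | **related** | **not related** |

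Only the last row depends on the reading. The either-agent reading is the plainer one, because SAP 6.0 uses the term for both drugs and the related-event table is by treatment, with itraconazole alone as one of the treatments. The SAP does not state it, however.

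**Step 3: missing answers.** If one of the two answers is missing, the SAP does not say whether the event's relationship counts as missing. Under a single flag, an imputed Yes for itraconazole would make the whole event related.

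**Step 4: what one reclassified subject does.** SAP 6.1 plans 14 subjects at the analysed dose and at least 12 completers. 1/14 = 7.1% and 1/12 = 8.3%. If the dose is raised, SAP 9.1.4 reports the four Cohort A subjects separately, and there 1/4 = 25%.

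**Step 5: illustration only.** Protocol 1.3 gives itraconazole rates of about 11% for nausea, 9% for rash and 5% for vomiting. The nausea and vomiting rates are from patients treated for systemic fungal infection, and rash is likewise reported in patients. Assuming that these rates carry over to n healthy subjects, the expected number is n × p and the chance of at least one is 1 − (1 − p)^n:

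- Nausea: 12 × 0.11 = 1.3 to 14 × 0.11 = 1.5; chance 75% to 80%.
- Rash: 12 × 0.09 = 1.1 to 14 × 0.09 = 1.3; chance 68% to 73%.
- Vomiting: 12 × 0.05 = 0.6 to 14 × 0.05 = 0.7; chance 46% to 51%.

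These figures count every case, including any in the run-in and any also rated related to balovaptan. The last row of the table in step 2 is a subset of them, and its size is not given anywhere.

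**The case against.** The strongest reply is that this is a gap in wording, not a demonstrated misclassification. Protocol 5.3.4 itself speaks of the study drug in the singular before requiring the answer per therapy, so the same singular in the SAP does not prove that the answers are merged. The SAP is to be read with the eCRF, layouts follow the contract research organization's standards, and Table 14.3.1.3 could in practice show per-drug categories. This stands: the outcome is an inference from the plain reading.

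Two stronger readings are tempting, and neither is supported.

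- A reader might infer that the rule of counting the most drug-related event merges the two answers. That rule chooses among repeat occurrences of one preferred term in a subject and treatment. It does not address two drug-specific answers to a single event.
- A reader might infer an undeclared departure from SAP 7.1, which says "There are no changes from the protocol". Table 3 governs how causality is assessed, and Protocol 6.5 promises no table by relationship, so there is no promised output from which the SAP departs.

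It is also fair that other outputs help. The all-TEAE table uses no attribution, and the itraconazole-alone column shows some of the inhibitor's own events. That column covers only four days of twice-daily dosing and one further morning dose, against 15 days of combination, so it does not replace per-drug attribution. Listing 16.2.7.1 may show both answers. The SAP does not say so, and a listing would not change the tables.

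Finally, Protocol 3.3.1 concedes that open-label knowledge may affect how causality is judged. Splitting attribution between two drugs taken together relies on that same judgement. This limits the benefit of the fix but does not remove it.

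**Conclusion.** The point holds as a low-severity, cheap improvement. The protocol requires that "causality will be assessed individually for each protocol-mandated therapy" during coadministration. The SAP has one relationship dimension and no rule for differing answers. On the plain reading, events rated related only to itraconazole would count as related in the combination column, so related would not mean the same thing there as in the balovaptan-alone column.

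The effect is confined to Tables 14.3.1.2 and 14.3.1.3, which are descriptive summaries for a secondary objective. The all-TEAE table and the primary PK analysis are unaffected.

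The number of events is unknown. A reader might infer from the itraconazole rates that such events would dominate the related-event table. The documents do not support that: the rates come from patients, Protocol 1.3 says that the gastrointestinal events may be reduced by dosing with food (as is done here) and that rash is more frequent in immunocompromised patients, and no rate of balovaptan-related events is given for comparison. What can be said is that in columns of 12 to 14 subjects one or two reclassified subjects would be visible. The conclusion rests on study drug covering both agents and on both answers being recorded as the protocol requires.

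**What to change.** Carry two relationship flags in ADAE, one for balovaptan and one for itraconazole. Present Tables 14.3.1.2 and 14.3.1.3 for events related to balovaptan and for events related to itraconazole, with an either-drug version as an option. State in SAP 17.1.1 which flag each table uses and how any combined category is formed, and apply the missing-relationship imputation to each drug separately.

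The protocol already requires the data. The cost is one or two more descriptive tables and a few sentences of text. The remaining limitation, that attribution is an open-label judgement, can be stated in a footnote to the tables.

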17.1.2 Deaths and Serious Adverse Events

A listing of deaths and other serious adverse events (SAE) will be provided by subject.

17.1.3 Laboratory Data

Clinical laboratory data will be presented using units from the study data tabulation model (SDTM) Controlled Terminology.

All laboratory data will be listed, including laboratory variables not listed in the protocol. A separate listing, including out-of-range values will also be provided. Normal ranges will be used directly from the clinical laboratory.

Descriptive statistics summarizing continuous laboratory results of clinical chemistry, hematology and urinalysis (observed and derived changes from baseline) by treatment and scheduled time will be provided.

17.1.4 Vital Signs

All vital signs data including derived changes from baseline will be listed.

Descriptive statistics will be provided to summarize vital signs including changes from baseline by treatment and scheduled time.

17.1.5 Electrocardiograms

All ECG parameters (including changes from baseline) and the corresponding abnormalities and physician's conclusions will be listed by subject.

The observed measurements for all ECG parameters (including T-wave, U-wave) and the corresponding abnormalities will be listed for all time points. The means of triplicate measurements for continuous parameters and the change from baseline of the mean triplicate measurements at each scheduled time point will be listed by subject.

Descriptive statistics will be provided to summarize mean continuous ECG parameters (observed and changes from baseline) by treatment and scheduled time. Physicians conclusion (normal /abnormal not clinically significant/abnormal clinically significant) will be summarized in a frequency table.

17.1.6 Columbia Suicide Severity Rating Scale

C-SSRS is a clinical tool used to assess the lifetime suicidality of a subject (C-SSRS lifetime version) as well as any new instances of suicidality (C-SSRS since last visit). It captures the occurrence, severity and frequency of suicide-related thoughts and behaviors during the assessment period. All individual C-SSRS results will be listed.

17.1.7 Other Observations Related to Safety

Abnormalities and changes in findings at the physical examinations will be listed.

Appendix 1: Glossary of Abbreviations

Glossary of Abbreviations:	
AE	Adverse event
ADAE	Adverse Event Analysis Dataset
ADaM	Analysis data model
ADPC	PK Concentrations Analysis Dataset
ADPP	PK Parameters Analysis Dataset
ADSL	Subject Level Analysis Dataset
BMI	Body mass index
BQL	Below the quantifiable limit
CDISC	Clinical Data Interchange Standard Consortium
CI	Confidence interval
CRU	Clinical research unit
C-SSRS	Columbia Suicide Severity Rating Scale
CSR	Clinical study report
CV	Coefficient of variation
DBP	Diastolic Blood Pressure
ECG	Electrocardiogram
eCRF	Electronic case report form
EDS	Early Development Services
FSH	Follicle-stimulating hormone
HIV	Human immunodeficiency virus
HBsAg	Hepatitis B virus surface antigen
HCV	Hepatitis C virus
ICH	The International Conference on Harmonization of Technical Requirements for Registration of Pharmaceuticals for Human Use
LLOQ	Lower limit of quantification
MedDRA	Medical Dictionary for Regulatory Activities
M2, M3	Metabolites
PK	Pharmacokinetic
QA'd	Quality assured
QC'd	Quality controlled
qd	Once daily
SAP	Statistical analysis plan

SAE	Serious adverse event
SBP	Systolic Blood Pressure
SD	Standard deviation
SDTM	Study data tabulation model
TEAE	Treatment-emergent adverse event
TFL(s)	Tables, figures and listings
WNL	WinNonlin

Appendix 2: Schedule of Assessments

	Screening	Period 1							Period 2											Follow-up					
		-1	1	2 to 8	9	10	11	washout (at least 7 days)	-1	1	2	3	4	5	6 to 11	12	13	14	15	16	17 to 19	20	21	14 to 21 days postdose	
Procedures																									
Informed consent	X																								
Inclusion and exclusion criteria	X	X																							
Demographic data	X																								
Medical history	X	X																							
Urine drug screen and urine alcohol test	X	X							X																
Urinalysis	X	X												X									X		X
Serology	X																								
Coagulation ^a	X																								
Pregnancy test ^b	X	X							X																X
Balovaptan administration ^c			X	X	X	X									X	X	X	X	X	X	X	X	X		
PK sampling for Balovaptan and metabolites M2 and M3 ^d			X	X	X	X	X								X		X	X	X	X	X	X	X		
Itraconazole administration ^e										X	X	X	X	X	X	X	X	X	X	X	X	X	X		
PK sampling for Itraconazole and hydroxyl-itraconazole ^f														X	X ⁿ						X	X			
Genotyping sample		X																							
Physical examination	X								X														X ^g	X	
Height, body weight and BMI ^h	X	X							X																

ⁱSee [Appendix 2](#) for specific ECG time points by study day

^jSee [Appendix 2](#) for specific vital signs time points by study day

^kPrior to breakfast

^lAt predose (breakfast will be provided 30 minutes before dosing and completed within approximately 15 minutes prior to balovaptan or itraconazole dosing), and at 5, 9, and 11.5 hours post dose

^mPredose

ⁿAssessments performed on Days 6, 8, and 10

^oAssessments performed on Day 17

^pTest performed about 3 hours after the morning dose of balovaptan. On Day 4 in Period 2, when only itraconazole is dosed, the timing of the orthostatic challenge test should correspond to 3 hours after the time of balovaptan dosing in Period 2.

Appendix 3: Schedule of PK Sampling, ECG, and Vital Signs Measurements

Procedure Study Day	Predose	Hours post dose											
		1	2	3	4	5	6	8	10	12	16	24	
Blood sampling balovaptan, M2, and M3													
Period 1													
Day 1, 3, 5, 8, 9	X ^a												
Day 10	X ^a	X	X	X	X	X	X	X	X	X	X	X ^b	X ^b
Period 2													
Day 6, 8, 10, 13, 14, 16, 18, 19	X ^a												
Day 15	X ^a	X	X	X	X	X	X	X	X	X	X	X ^c	X ^c
Day 20	X ^a	X	X	X	X	X	X	X	X	X	X	X ^d	X ^d
Blood sampling itraconazole and hydroxyl-itraconazole													
Period 2													
Day 5	X ^a		X		X			X					
Day 6, 8, 10, 14, 15, 16, 18, 19	X ^a												
Day 20	X ^a		X		X			X					X ^c
12-lead electrocardiograms													
Period 1													
Days 1 and 10	X												
Period 2													
Day 1	X ^e												
Day 5, 6, 8, 10, 13, 15, 17, 20	X				X								
Vital signs													
Period 1													
Day 1	X												
Day 11 ^f													
Period 2													

Procedure Study Day	Predose	Hours post dose										
		1	2	3	4	5	6	8	10	12	16	24
Day 1	X ^e											
Day 6	X	X	X		X			X		X		
Day 8, 10, 13, and 17	X				X							
Day 15	X	X	X		X			X		X		
Day 21 ^f												

^a10 minutes predose (or time matched, when not dosed)

^bDay 11

^cDay 16

^dDay 21

^ePre-AM dose

^fPrior to discharge

Appendix 4: List of End of Text Outputs

List of End of Text Tables and Figures:		
Output	Title	Population Set
Section 14.1 Disposition and Demographic Data		
Table 14.1.1	Summary of Subject Disposition	Safety
Table 14.1.2.1	Summary of Demographics	Safety
Table 14.1.2.2	Summary of Demographics (if applicable)	PK
Section 14.2 Pharmacokinetic Data		
Table 14.2.1	Individual Values and Descriptive Statistics of Balovaptan Plasma Concentrations by Treatment, Analysis Day and Time-Point	PK
Table 14.2.2	Individual Values and Descriptive Statistics of Balovaptan Plasma Parameters by Treatment and Analysis Day	PK
Table 14.2.3	Individual Values and Descriptive Statistics of Balovaptan Metabolite (M2 and M3) Plasma Concentrations by Treatment, Analysis Day and Time-Point	PK
Table 14.2.4	Individual Values and Descriptive Statistics of Balovaptan Metabolite (M2 and M3) Plasma Parameters by Treatment and Analysis Day	PK
Table 14.2.5	Individual Values and Descriptive Statistics of Itraconazole and OH-Itraconazole Plasma Concentrations by Treatment, Analysis Day and Time-Point	PK
Table 14.2.7	Statistical Analysis of the effect of Itraconazole on Balovaptan	PK
Table 14.2.8	Statistical Analysis of the effect of Itraconazole on Balovaptan Metabolites (M2 and M3)	PK
Figure 14.2.10	Geometric Mean Balovaptan Plasma Concentrations versus Time by Treatment and Analysis Day (Linear and Semi-Logarithmic Scale)	PK
Figure 14.2.11	Geometric Mean Balovaptan Metabolite (M2 and M3) Plasma Concentrations versus Time by Treatment and Analysis Day (Linear and Semi-Logarithmic Scale)	PK
Figure 14.2.12	Geometric Mean Itraconazole and OH-Itraconazole Plasma Concentrations versus Time by Treatment and Analysis Day (Linear and Semi-Logarithmic Scale)	PK
Figure 14.2.13	Combined Individual Balovaptan Plasma Concentrations versus Time by Treatment and Analysis Day (Linear and Semi-Logarithmic Scale)	PK
Figure 14.2.14	Combined Individual Balovaptan Metabolite (M2, M3) Plasma Concentrations versus Time by Treatment and Analysis Day (Linear and Semi-Logarithmic Scale)	PK
Figure 14.2.15	Combined Individual Itraconazole and OH-Itraconazole Plasma	PK

	Concentrations versus Time by Treatment and Analysis Day (Linear and Semi-Logarithmic Scale)	
Figure 14.2.16	Individual Balovaptan Plasma Concentrations versus Time in Days by Treatment (Linear and Semi-Logarithmic Scale)	Safety
Figure 14.2.17	Individual Balovaptan Metabolite (M2, M3) Plasma Concentrations versus Time in Days by Treatment (Linear and Semi-Logarithmic Scale)	Safety
Figure 14.2.18	Individual Itraconazole and OH-Itraconazole Plasma Concentrations versus Time in Days (Linear and Semi-Logarithmic Scale)	Safety
Figure 14.2.19	Geometric Mean Trough Balovaptan Plasma Concentrations versus Time by Treatment (Linear and Semi-Logarithmic Scale)	PK
Figure 14.2.20	Geometric Mean Trough Balovaptan Metabolite (M2, M3) Plasma Concentrations versus Time by Treatment (Linear and Semi-Logarithmic Scale)	PK
Section 14.3 Safety Data		
Section 14.3.1 Adverse Events		
Table 14.3.1.1	Summary of TEAEs for Each System Organ Class and Preferred Term (Number and Percentage of Subjects) by Treatment	Safety
Table 14.3.1.2	Summary of Related TEAEs for Each System Organ Class and Preferred Term (Number and Percentage of Subjects) by Treatment	Safety
Table 14.3.1.3	Summary of TEAEs for Each System Organ Class and Preferred Term (Number and Percentage of Subjects) by Treatment and Relationship to Study Drug	Safety
Table 14.3.1.4	Summary of TEAEs for Each System Organ Class and Preferred Term (Number and Percentage of Subjects) by Treatment and Severity	Safety
Section 14.3.2 Lists of Deaths, Other Serious and Significant Adverse Events		
Table 14.3.2.1	Listing of Deaths and Other Serious Adverse Events	Safety
Section 14.3.3 Clinical Laboratory		
Table 14.3.3.1	Listing of Abnormal Laboratory Values	Safety
Table 14.3.3.2	Descriptive Statistics of Clinical Laboratory Results - Hematology	Safety
Table 14.3.3.3	Descriptive Statistics of Clinical Laboratory Results – Serum Chemistry	Safety
Table 14.3.3.4	Descriptive Statistics of Clinical Laboratory Results - Urinalysis	Safety
Section 14.3.4 Other Safety		
Table 14.3.3.1	Descriptive Statistics of Vital Signs	Safety
Table 14.3.3.1	Summary of 12-Lead Electrocardiogram	Safety

List of End of Text Listings:	
Output	Title
Section 16.2.1 Disposition	
Listing 16.2.1	Subject Disposition
Section 16.2.2 Protocol Deviations	
	Not part of TFL – Reserved for protocol deviations in CSR
Section 16.2.3 Excluded Subjects	
Listing 16.2.3.1	Analysis Sets
Section 16.2.4 Demographics and Baseline Characteristics	
Listing 16.2.4.1	Subject Demographics (including genotype)
Listing 16.2.4.2	Medical History
Listing 16.2.4.3	Prior and Concomitant Medications
Listing 16.2.4.4	Drug and Alcohol Screen
Listing 16.2.4.5	Serology Test Results
Listing 16.2.4.6	Pregnancy and Serum FSH Test Results
Listing 16.2.4.7	Genotyping Results
Section 16.2.5 Compliance and Drug Concentration Data	
Listing 16.2.5.1	Study Dates
Listing 16.2.5.2	Study Drug Administration
Listing 16.2.5.3	Deviations from Inclusion/Exclusion criteria
Listing 16.2.5.4	PK Blood Sampling Time Deviations and Comments
Listing 16.2.5.5	Food Intake
Section 16.2.7 Adverse Events Data	
Listing 16.2.7.1	Adverse Events
Listing 16.2.7.2	Adverse Events Leading to Withdrawal
Section 16.2.8 Laboratory Data	
Listing 16.2.8.1	Clinical Laboratory Results – Hematology
Listing 16.2.8.2	Clinical Laboratory Results – Chemistry
Listing 16.2.8.3	Clinical Laboratory Results – Urinalysis
Listing 16.2.8.4	Clinical Laboratory Results – Coagulation

Section 16.2.9 Other Safety Data	
Listing 16.2.9.1	Vital Sign Results
Listing 16.2.9.2	12-Lead Electrocardiogram Results
Listing 16.2.9.3	Abnormalities and Changes in Findings at the Physical Examinations
Listing 16.2.9.4	Columbia-Suicide Severity Rating Scale

Other Appendix Outputs:	
Output	Title
Appendix 16.1.7	Randomization
Appendix 16.1.9.2	Statistical Appendices

Document History

Version Date	Modified/Reviewed By	Brief Summary of Changes
03-Aug-2018		Created from EDSREP 009 T 01 G template
28-Sep-2018		Sponsor comments included
09-Nov-2018		Additional sponsor addressed
14-Nov-2018		Statistical model for DDI analysis clarified after discussion with [REDACTED]
